12.3.4.1 Relationship Between "Intensity" (Severity) and Seriousness in Characterizing Clinical AEs

Intensity (severity) and seriousness are distinct and independent items, with some interrelationship. By definition, clinical events assessed as SAEs meeting criteria for "death" would be Grade 5 and those meeting criteria for "hospitalization" or "life-threatening" would be Grade 4. Typically, events assessed as SAEs based on associated "significant disability" or being "medically important" would be Grade 3 or Grade 4. However, a clinical event may be assessed as Grade 3 and *not* qualify as an SAE; for example, a patient with a history of migraine headaches could have an episode that restricted them to bed for several hours but responded to the usual treatment, ran its usual course and had no sequelae.

**Confidential and Proprietary** 

[name] 5/31/15 10:25 AM

Deleted: Table 12-2

### 12.3.5 Management of Study Drug

For each AE the Investigator will indicate which one of the following actions regarding the administration of study drug (study treatment) was taken because of that AE:

- **Drug withdrawn (discontinued)** study drug was stopped permanently due to the AE;
- Drug interrupted study drug regimen was modified temporarily, including one or more doses were not administered, but drug was not stopped permanently;
- **Dose reduced (decreased)** study drug regimen was modified by subtraction, i.e., by decreasing the frequency, strength or amount;
- **Dose Increased** study drug regimen was modified by addition, i.e., by increasing the frequency, strength or amount;
- Dose not changed (No action taken) no change in the administration of study mediation.

### 12.3.6 Actions Taken for Management of AE

AEs will be followed and managed by the Investigator, including obtaining any supplemental studies needed to define the nature and/or cause of the event (e.g., laboratory tests, diagnostic procedures, consultation with other health care professionals).

For each AE the Investigator will categorize as follows the actions taken to manage the AE:

- *Concomitant medication* one or more medications (prescription or over-the-counter) were started or increased in dose; non-medication actions may *also* have been ordered.
- *Other action only* non-medication action(s) were ordered as management of the AE (e.g., bed placed in Trendelenburg position, warm compresses applied to IV access site).
- *No action* no actions were ordered for management of the AE.

### 12.3.7 Outcome

**Follow-up of AEs.** If possible, AEs will be followed until resolved (synonyms: recovered, recuperated, ended) either with or without sequelae, including for subjects who prematurely discontinue study participation. For AEs that are assessed as not drug-related and are not resolved at the End-of-Study visit, follow-up may be limited with the approval of the Medical Monitor.

Outcome of AEs. The outcome of each event will be described using the following categories:

- *Resolved (recovered) without sequelae* the event resolved and subject returned to baseline;
- **Resolved (recovered) with sequelae** the event resolved but the subject is left with residual problems (e.g., functional deficits, pain);
- **Resolving (recovering)** at the last observation, the event was improving;
- Not Resolved (not recovered) at the last observation, the event was unchanged;
- **Death (Fatal)** to be used for the *one* AE which, in the judgment of the Investigator, was the *primary* cause of death;
- *Unknown* there were no observations after the onset (initial observation or report) of the event.

Note: Resolving and Not Resolved may also be used for AEs that were unresolved at the time a subject died, but were *not* assessed as the primary cause of death.

Page 51 of 75 Date: 30 March 2015

#### 12.3.8 Date and Time of Outcome

For each class of outcome as defined above, Table 12- $3_4$  indicates the date and time to be recorded. As discussed in detail for date / time of onset (see Section 12.3.2), determining the date / time an event resolved (ended) should reflect the type of event and the source of the information.

#### Table 12-3. Date and Time of Outcome for AE by Outcome Class

Outcome assigned to AE	Date and Time to be Recorded
Resolved (with or without sequelae)	Date and time event observed or reported as resolved
Death	Date and time of death
Resolving or Not Resolved	Date and time of last observation
Unknown	None (see definition above)

#### 12.4 Reporting of Serious Adverse Events

#### 12.4.1 Where to Report SAEs

SAE reporting forms with detailed instructions will be provided during training. Serious adverse events will be entered immediately into the electronic Source Tablet prompting automatic notification of all relevant study personnel, including the Medical Monitor. The CRO will work with the Site to collect any additional data needed to further evaluate the SAE. Reports and supporting materials relating to SAEs should be submitted as scanned documents. The Site will enter the data required into the electronic Source Tablets. Data received from outside sources such as local labs or a Discharge Summary will be stored electronically.

The Investigator will notify the IRB of SAE's based on reporting requirements. Contact information is provided in Section 17.

#### 12.4.2 Procedures for Reporting SAEs to the Sponsor

The *initial notification* should be completed in the eSource for each SAE within 24 hours of the time the Investigator (or the Investigator's designee) becomes aware that the event has occurred and will include the following items of information (any items not available should be explicitly noted):

- protocol number, study site, subject number;
- Investigator's name, address, and contact information (phone, fax, email);
- · description of the event (i.e., date and time of onset, initial assessment, treatments and course);
- current status of the subject and the event;
- criteria by which the event was assessed as serious;
- date of the first injection of study drug;
- date of the last injection of study drug prior the event;
- assessment of relationship of study drug to the event;
- whether the study drug was discontinued or adjusted as a result of the event.

The *initial full report*, signed by the Investigator, will be submitted within two days for death and lifethreatening events and within four days for all other SAEs; the report will include all of the above information *plus* the following items:

- narrative summary of the event to include specific information that will assist in understanding the event, e.g., relevant medical history, co-morbid conditions, physical exam, diagnostics, assessment, treatments (including concomitant medications), response to treatment, course, and outcome (if known);
- copy of the completed AE page of the CRF (or completion of online data entry);
- copies of relevant medical reports including diagnostic procedures (e.g., laboratory, ECG, x-ray), surgical procedures, and consultations.

**Confidential and Proprietary** 

[name] 5/31/15 10:25 AM **Deleted:** Table 12-3

DAR-901	Page 52 of 75
Protocol DAR-901-MDES, Version 4.1	Date: 30 March 2015

Thereafter, signed *supplemental reports* will be submitted as any additional information (e.g., more definitive outcome regarding events previously reported as ongoing or unknown outcome) becomes available to the Investigator (either directly or as a result of investigation into a query).

### 12.4.3 Requirements for Expedited and Periodic Reporting of Adverse Events

SUSARs are required to be reported rapidly to the DRC, regulatory authorities and to EC/IRBs (within seven days for fatal or life-threatening SUSARs; within 15 calendar days for all other SUSARs). There are varying requirements for periodic (annual or semi-annual) reporting of all SUSARs and, in some cases, all SAEs. The Sponsor and the Investigator will work together to meet these reporting requirements.

### 12.4.4 Notification of SAEs to the Investigator by the Sponsor

In accordance with regulatory requirements, the Sponsor will notify the Investigator of the occurrence of SUSARs reported by other Investigators in this or in other studies involving the study drug. The Investigator will promptly inform his/her IEC of such communications from the Sponsor and will document that notification in the Investigator's Regulatory Binder.

### 12.5 Sponsor Guidance for Grading of Injection Site Reactions

As detailed in Section 5.5, the adverse events associated with intradermal injection of SRL 172 were primarily injection site reactions similar to, but generally milder than, reactions to BCG vaccination, which has been used world-wide for over 70 years. Further, DAR-901 is a heat-inactivated vaccine with no living organisms, so the rare invasive BCG complications of lymphangitic or hematogenous spread are not under consideration, even in HIV-infected persons.

### 12.5.1 Definitions of the Most Commonly Expected Systemic Vaccine-related Symptoms

- Fever: elevated temperature documented by any route during a visit or by the subject at home.
- Feverish: subjective fever reported by the subject, but not documented.
- Malaise, myalgia, "flu-like" symptoms: will be defined consistent with routine clinical practice.

### 12.5.2 Definitions of the Most Commonly Expected Injection Site Symptoms

- Tenderness: discomfort elicited when the area is touched either intentionally or accidently.
- Pain: discomfort or unpleasant feeling (e.g., headache, stubbed toe) experienced while at rest or with activity; in addition to location, the patient's description may include intensity as well a distinctive quality (e.g., burning, stabbing). In the SRL 172 trials (see Section 5.5), these events were reported as "sore arm."
- Pruritus (itch): an unpleasant sensation that evokes the desire or reflex to scratch. (In contrast, pain and tenderness evoke a reflex to withdraw.)

### 12.5.3 Definitions of the Most Commonly Expected Injection Site Findings

- Erythema: reddening of the skin.
- Desquamation: skin coming off in scales, often patchy or circumferential; maximum linear diameter will be recorded only if the area of involvement is a continuous patch.
- Induration: an area of skin that is thicker, firmer than usual. Will be used to include both the related terms papule / nodule (a solid raised lesion with distinct borders, <1 cm diameter) and plaque (papule-like lesion, >1 cm), since diameter will be recorded independently.
- Vesicle / Blister: a sub-epidermal collection of clear fluid
- Pustule: a sub-epidermal collection of white or yellow fluid up to 2.5 cm diameter that based on appearance is presumed to be "pus", i.e., to contain neutrophils. Commonly seen after intradermal injection of BCG or heat-killed mycobacteria, but rarely infected with pyogenic bacteria.
- Erosion: the loss of the surface of the skin; typically results in a shallow moist or crusted lesion. In the studies with SRL 172 (see Section 5.5), this process was reported as "skin breakdown".

- Ulceration: full thickness loss of epidermis, with erosion into dermal or deeper tissue; commonly crusted or with granulation.
- Crust: dried material covering an erosion or ulceration; may be white or colorless if composed of plasma or exudate, or darker if small amounts of blood are present.
- Eschar: hard dry plaque covering an ulcer, implying underlying tissue necrosis
- Abscess: a sub-epidermal collection of white or yellow fluid greater than 2.5 cm diameter that based on appearance is presumed to be "pus", i.e., to contain neutrophils. If closed, the lesion is typically fluctuant, that is yields to palpation consistent with containing fluid. Abscesses may open and drain spontaneously or may be incised and drained by the investigator. Abscesses will be classified as "Sterile" or "Infected (Pyogenic)" (see below).
  - If an abscess is incised by the investigator, a fresh culture should be obtained. Open lesions
    have a high likelihood of contamination and culture is generally only useful if there are other
    findings, such as surrounding cellulitis or acute systemic symptoms.
  - The investigator may prescribe topical or systemic antibiotics based on their judgment of the risk of current or potential pyogenic involvement. The expected pathogens would be *Staphylococcus aureus* or β-hemolytic streptococci.
- Sterile Abscess: In a recent prospective, active surveillance of BCG immunization, sterile abscess was reported in 3.6% (18/504) persons over 6 months of age [18]. In the DarDar trial, sterile abscess was observed in 0.3% of HIV-infected adults who received SRL 172 [1]. Neither study reported any pyogenic abscesses. Sterile abscesses are typically not accompanied by surrounding erythema, warmth, or marked tenderness, or by fever or regional lymphadenopathy [19].
- Infected Abscess: An abscess due to pyogenic bacteria, typically *Staphylococcus aureus*. In addition to documented positive cultures, pyogenic abscess is expected to be accompanied by at least one of the following: surrounding erythema, warmth, or marked tenderness. Infected abscess also often present with fever and regional lymphadenopathy.
- Scar: an area of fibrous tissue that replaces normal skin after injury; a natural sequela of wound repair and healing. Often associated with mild discoloration.

### 12.5.4 Visit Assessment of Injection Site Reactions and Other Post-Dosing Events

At each visit specified in Sections 2.9 and 12.2, the subject will have vital signs obtained, be interviewed by study personnel regarding symptoms and other events, and examined by the Investigator.

Treatment-emergent changes in vital signs will be graded using the criteria shown in Table 20-2, which are taken from FDA Guidance [20].

Subjects will be explicitly asked about systemic and local symptoms (see Sections 12.5.1 and 12.5.2, respectively), any interference with daily activities, and any treatment required. Symptoms will be graded using the functional criteria shown in Table 12-4.

Investigator will examine all of the prior injection sites and then:

- Record the presence or absence of the physical findings defined in Section 12.5.3;
- For any findings present, record the maximum linear diameter in mm;
- Pain, erythema, and induration will be graded as shown in Table 12-5, taken from FDA Guidance [20]; other ISRs characteristics will be graded using the functional criteria shown in Table 12-4.
- Considering *all* the findings present, the investigator grade the *overall* intensity (severity) of the ISR as per Table 12-4.
- This grade should be "static", that is, based upon the impact and management of the ISR at the time, without reference to previous observations for the subject.
- Subjects will be asked for permission to photograph the ISR if it is assessed as Grade 2 or higher, is accompanied by systemic symptoms, or is managed with prescription medication (e.g., systemic antibiotics or prescription analgesics). Photographs are completely optional and may be declined by the subject without impacting any other aspects of the protocol.

**Confidential and Proprietary** 

[name] 5/31/15 10:25 AM **Deleted:** Table 20-2

[name] 5/31/15 10:25 AM Deleted: Table 12-4

[name] 5/31/15 10:25 AM Deleted: Table 12-5 [name] 5/31/15 10:25 AM Deleted: Table 12-4 [name] 5/31/15 10:25 AM Deleted: Table 12-4

#### Table 12-4. Grading of Vaccine-Related Adverse Events

Characteristic	Grade 1	Grade 2	Grade 3
Impact on ADL	No limitations in ADL	Some limitations in age-appropriate instrumental ADL	Some limitations in self-care ADL
Medication	None or self-medication with	Prescription meds offered;	Requires prescription meds; relief may be partial
intervention	OTC meds	provide relief	
Interventions other than medication	Minimal, local, or	Minimal, local, or	Requires hospital facilities
	non-invasive	non-invasive	for <24 hr

This Table is intended to provide guidance; the investigator should use judgment in assigning an intensity grade to an ISR. In some instances a single characteristic may determine the grade; in other instances, the overall pattern may be considered more appropriate.

#### Table 12-5. Grading of Common Injection Site Reactions

Local Injection Site Reaction	Grade 1	Grade 2	Grade 3	Grade 4
Pain	Present but does not interfere with activity	Repeated use of non-narcotic pain reliever >24 hours or interferes with activity	Any use of narcotic pain reliever or prevents daily activity	Emergency room (ER) visit or hospitalization
Erythema a	2.5 – 5 cm	5.1 – 10 cm	> 10 cm	[C]
Induration/Swelling b	2.5 – 5 cm and does not interfere with activity	5.1 – 10 cm or interferes with activity	> 10 cm or prevents daily activity	[c]

a. Erythema (Redness) should be measured at the maximal diameter and the measurement should be graded and also recorded as a continuous variable.

b. Induration (Swelling) should be measured at the maximal diameter and the measurement will also be recorded as
a continuous variable; the event should be graded using the functional scale as well as the actual measurement.
 c. Note that Erythema and Induration, in and of themselves, are not "life-threatening (Grade 4)" events; however, they
measurements and near a cylinitic darmatilia or nearsoin that beying the functional scale as the actual graded graded

may progress to new events, such as exfoliative dermatitis or necrosis, that should be recorded and graded separately.

### 12.5.5 Subject Monitoring of Injection Site Reactions

As specified in Sections 2.9 and 12.2, between scheduled visits, subjects will be contacted by telephone twice weekly to monitor systemic and local reactions to vaccine administration. The calls will be conducted using a detailed script and data collection form to be sure that both expected and uncommon events are elicited and recorded. The process will be facilitated by providing subjects with the following:

- an electronic oral thermometer to monitor temperature daily
- paper rulers with which to measure any ISRs
- a diary on which to record temperature, systemic symptoms, and local ISRs.

Figure 20-1, shows the Subject Diary Instructions page; Figure 20-2, shows a sample record page.

During the telephone follow-up calls, study staff will collect the information recorded on the subject's diary / memory aid for each day since the last visit / call completed with the subject. Subjects will then be asked the following questions:

- Have you had any other reactions or events other than those indicated on the diary?
- How they are feeling today (the day of the call)?
- Collect details of any spontaneously reported symptoms.
- Today, are you having any .... (ask specifically the symptoms noted on the dairy, unless already reported by the subject)?
- · Have you taken any over-the-counter medication since the last visit/call?

**Confidential and Proprietary** 

[name] 5/31/15 10:25 AM Deleted: Figure 20-1 [name] 5/31/15 10:25 AM Deleted: Figure 20-2

- If so, for what symptoms? Which medicine? What dose? What frequency?
- Did the medication relieve your symptoms?
- Have you taken any prescription medication since the last visit/call?
  - If so, what symptoms? Which medicine? What dose? What frequency?
  - Did the medication relieve your symptoms?
- Have any of the symptoms interfered with your usual daily activities, such as exercise, playing the piano, holding a book to read?
  - Have you been unable to do any of your usual daily activities?
  - Have you been unable to attend work or classes?
- Have any of these symptoms interfered with activities related to taking care of yourself, such as dressing, cooking, brushing your teeth, going to the bathroom.
  - Have you required assistance for any of these activities?

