# 7.5.1 Definition of a Dose-Limiting Toxicity (DLT) Event

A DLT systemic clinical event is defined as a treatment-emergent systemic clinical event that meets **all** of the following criteria:

- is assessed by the investigator as related or possibly related to study drug (see Section 12.3.3);
- is of severity (see Section 12.3.4) Grade 2 or higher;
- is of duration >48 hours.

A DLT injection site reaction (ISR) is defined as an event that meets both of the following criteria:

- occurs at the injection site;
  - is of severity Grade 3 or higher.

A DLT *laboratory event* is defined as a confirmed, treatment-emergent laboratory finding that meets **both** of the following criteria:

- is *not* considered consistent with a concurrent clinical event that is assessed as not related or unlikely related to study drug (e.g., an accidental injury, new ART); *and*
- based on pre-specified toxicity criteria (see Section 12.5.5), represents an increase of two Grades or more compared to pre-treatment baseline value.

A subject who experiences a DLT event will not receive further doses of study drug. Unblinding may be performed to determine if a DLT event has occurred in a subject receiving DAR-901.

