### 12.3.4 Intensity (Severity)

The intensity (synonym: severity) of clinical AEs (i.e., symptoms reported by the patient and/or signs observed by the investigator) will, in general, be assessed by the Investigator using the five-level grading system (Table 12-2; adapted from CTCAE v4.02 [17]). The system reflects the duration of the event, its impact on the subject's activities, the level of medical intervention required, and, for events assessed as related or possibly related to study drug, the action taken with study drug. The Table below is intended to provide guidance; the investigator should use judgment in assigning an intensity grade to an event. In some instances a single characteristic may determine the grade; in other instances, the overall pattern may be considered more appropriate.

For this purpose, activities of daily living (ADL) are classified into two subsets:

- *Instrumental ADL* e.g., preparing meals, shopping for groceries or clothes, using the telephone, managing money;
- Self-care ADL e.g., bathing, dressing and undressing, feeding self, using the toilet, taking medications, and not being bedridden.

Note that the Sponsor provides specific guidelines for grading injection site reactions (see Section 12.5).

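### The telephone script lists cooking as self-care while Section 12.3.4 classes meal preparation as instrumental, so a Grade 2 injection-site reaction may be read as Grade 3

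*Protocol*

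**What the plan says.** Section 12.3.4 of the protocol divides activities of daily living into two sets. The instrumental set is illustrated by "e.g., preparing meals, shopping for groceries or clothes, using the telephone" and managing money. The self-care set is illustrated by "e.g., bathing, dressing and undressing, feeding self, using the toilet, taking medications" and not being bedridden. Eating is in the self-care set; preparing the food is in the other.

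Table 12-4, the scale for vaccine-related events, uses these terms without redefining them. Its Grade 2 entry for impact on ADL is "Some limitations in age-appropriate instrumental ADL" and its Grade 3 entry is "Some limitations in self-care ADL". Table 12-2, the general scale, draws the line in the same place.

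The telephone questions at the end of Section 12.5.5 ask first whether symptoms have "interfered with your usual daily activities, such as exercise, playing the piano, holding a book to read", with follow-ups on inability to do usual activities and on missing work or classes. They then ask whether symptoms have "interfered with activities related to taking care of yourself, such as dressing, cooking, brushing your teeth" or using the bathroom, with a follow-up on needing assistance.

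Under Section 7.5.1, an injection-site event is a DLT if it "is of severity Grade 3 or higher". There is no duration or relatedness condition. A subject with a DLT receives no more study drug.

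**The concern.** The script and the severity scale place the same activity on opposite sides of the line between Grade 2 and Grade 3. For an injection-site reaction, that is also the DLT line.

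If a cooking limitation were carried through as self-care, the subject's dosing would end and the subject would count toward the two DLTs in a dose group that bring prompt review by the Dose Review Committee (Section 7.7). The event would also enter the safety description as Grade 3, and Section 14.3 analyses adverse events by intensity. A subject stopped for a DLT counts as complete (Section 7.5.2), while Section 7.6.2 provides replacement only for subjects who are not complete. A vaccinee lost this way would therefore not be made up, in a group with 10 DAR-901 recipients at most.

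**Working it through.** The protocol states no figure on this point, so the check is mainly a comparison of its sections.

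**1. Where cooking belongs.**

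| Source | Group that contains cooking or meal preparation |
|---|---|
| Section 12.3.4 | Instrumental (first example given) |
| Section 12.5.5, telephone questions | Taking care of oneself, beside dressing, brushing teeth and using the bathroom |

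These cannot both hold.

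**2. What the difference is worth.** A reaction that limits only cooking is Grade 2 under Section 12.3.4 and the ADL row of Table 12-4. Under the script's grouping, the same row reads Grade 3. The gap is one grade.

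**3. Which grades are exposed.** Section 12.5.4 sends symptoms, and the overall grade of the injection-site reaction, to Table 12-4. It sends pain, erythema and induration to Table 12-5, where interference with activity is Grade 2 and prevention of daily activity is Grade 3, with no instrumental/self-care split. The error can therefore enter through the Table 12-4 symptom grade and the overall grade, but not through Table 12-5.

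**4. What the answer reveals.** One question covers dressing, cooking, brushing teeth and using the bathroom. As worded, a positive answer does not show which was limited.

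**5. Where the call matters most.** After Doses 1 and 2, Table 2-2 schedules no clinic visit between day +7 and the next dose; days +10 to +28 are covered by telephone. A reaction that comes and goes in that window may be known only from the call and the diary.

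**6. Scale, for illustration only.** Let q be the probability that a subject has a Grade 2 reaction recorded as Grade 3 solely because of the cooking item. The protocol gives no value, so q is assumed. With n = 10 DAR-901 recipients (cohorts A1 to A3 in Table 2-1) and independent subjects:

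- P(at least one) = 1 − (1 − q)^10
- P(at least two) = 1 − (1 − q)^10 − 10q(1 − q)^9

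| Assumed q | At least one | At least two |
|---|---|---|
| 1% | 9.6% | 0.4% |
| 2% | 18.3% | 1.6% |
| 5% | 40.1% | 8.6% |
| 10% | 65.1% | 26.4% |

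The table shows what a given q would imply. It says nothing about what q is.

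**The case against.** The strongest reply is that nothing in Section 12.5.5 assigns a grade. The script collects answers and the investigator grades. Table 12-4 describes itself as guidance, asks for judgment and lets the overall pattern decide. Section 12.5.4 places injection-site grading at visits, where the investigator examines the sites. An investigator who applies the Section 12.3.4 definitions and knows that only cooking was affected would assign Grade 2. The data collection form used on the calls is not in the protocol text and may record which activity was limited. All of this stands, and it limits the point to a possible misreading. What remains is that judgment cannot recover a detail that was never recorded, and the script as written does not ask for it.

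A reader might infer several stronger things that the protocol does not support:

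- **That a positive answer is itself the Grade 3 criterion.** No section says so.
- **That Grade 2 interference is never asked about.** The usual-activities question and its follow-ups cover it. Its examples are only illustrations, although none comes from the Section 12.3.4 instrumental list.
- **That a false-DLT rate can be computed.** Sore arm followed 4% (Study 004) to 37% (the top of the range in HIV-positive subjects in Study 005) of SRL 172 doses. Assume that 5% to 20% of sore arms limit cooking but not self-care, that every such answer is graded 3, and that the three doses are independent. Then q = 1 − (1 − 0.04 × 0.05)^3 = 0.6% at the low end and 1 − (1 − 0.37 × 0.20)^3 = 20.6% at the high end, and P(at least two of 10) runs from 0.2% to 64%. The share is invented, and the second assumption contradicts the role of investigator judgment, so for any assumed share the result is at most a ceiling. The sore-arm rates used come from HIV-infected subjects, while the groups of 10 are HIV-negative.
- **That two such events would stop a dose group.** Section 7.7 requires notification and review, not an automatic stop.
- **That systemic DLTs are affected in the same way.** They already start at Grade 2 (with relatedness and duration conditions), so a shift from 2 to 3 does not change whether that severity condition is met.

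**Conclusion.** The inconsistency is real: cooking is self-care in the telephone script and instrumental in the severity definitions, and Table 12-4 separates the two by one grade at the injection-site DLT line. A positive answer due only to cooking could raise the Table 12-4 symptom grade or the overall injection-site grade from 2 to 3. That requires the answer to be read as a self-care limitation without further probing, and the investigator to let it decide the grade. The protocol neither directs this nor guards against it in the script. The frequency is unknown and cannot be derived from the protocol. Severity: minor. It is worth correcting because the DLT count and the Grade 3 tabulation are safety measures in small groups.

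**What to change.** Reconcile the Section 12.5.5 questions with Section 12.3.4:

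- Move cooking to the question on usual activities, and give that question the instrumental examples from Section 12.3.4.
- Limit the self-care question to the self-care examples from Section 12.3.4.
- For each positive answer, record which activity was limited.
- Re-check any Grade 3 injection-site grade that rested on the existing self-care question alone.

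The script should not say that only the self-care question leads to Grade 3, because Tables 12-2 and 12-4 also reach Grade 3 through their medication and intervention rows. No grading threshold, DLT definition or dosing rule needs to change. The cost is one wording edit to the script and the electronic source form, one added field if the form lacks it, and a short review of existing Grade 3 records. No extra calls or staff are needed.
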